## **Data security**

-Study data will be collected and managed using REDCap electronic data capture tools. REDCap (Research Electronic Data Capture) is a secure, web-based application designed to support data capture for research studies, providing: 1) an intuitive interface for validated data entry; 2) audit trails for tracking data manipulation and export procedures; 3) automated export procedures for seamless data downloads to common statistical packages; and 4) procedures for importing data from external sources. Identifiable information will be stored in password protected directory accessible only by study personnel. Finally, no identifiable information will be shared outside of our institution and all non-identifiable information will be pooled and released as a group for the final study after statistical analysis is complete. After the completion of the statistical analysis phase and a sufficient length of time, the file containing the patients' MRNs and study specific unique numerical identifiers will be deleted. Patient MRN and unique study specific identifier will be kept until completion of data analysis or >2 years, whichever is greater. The file containing study specific identifier and other study, as well as pooled statistics data, will be kept for a period of greater than 3 years per policy to allow additional statistical analysis as may be required for final manuscript revisions. Every attempt to obtain and maintain a complete and thorough record of data points will be made by the study staff. In the event that any data is unable to be obtained from the usual protocol source, every attempt to obtain the data from additional electronic medical record sources will be made. If no data is obtainable, said data point will not be placed in statistical analysis and reported as such.

No paper records will be kept other than the consent forms which will be kept in a locked cabinet in a locked office

### **Data and Safety Monitoring**

-Data and safety monitoring will be performed by the primary investigators throughout the study to ensure all above policies are being followed. Upon receipt of the study drug, patients will be reminded of contact information to reach investigators with any questions or concerns. They will be monitored closely in the hospital for any abnormalities which is standard for perioperative care. Investigators will again address any questions or concerns during the scheduled postoperative telephone follow up to discuss the questionnaire. The primary investigators will meet monthly to review patient enrollment and potential adverse events. Any unexpected or significant adverse event may prompt a preliminary statistical analysis and/or immediate halt in enrollment or cancellation of the study.

-Safety monitoring/event reporting: study investigators will actively monitor for unanticipated problems, adverse events, or protocol deviations, with specific emphasis on any events involving risk to subject or others. Record of these events will be kept in the Safety Monitoring Log. Monitoring will take place during preoperative communication with patient, during hospital stay, at the follow-up phone call, and in the postoperative period. In addition to monitoring and record keeping, events will be reported as appropriate. Unanticipated problems and any adverse events that may change the risk/benefit ratio will be reported to the IRB within 3 days of discovery per institutional guidelines. Serious adverse events will be immediately reported to the IRB and the patient's primary provider as soon as investigator is aware of the incident. Any adverse events that are felt to alter the risk/benefit ratio of the study may prompt a review and revision of study protocol and/or consent form. Non-serious adverse events will be kept in the Safety Monitoring Log.

## **Statistical considerations**

-Data will be evaluated with descriptive statistics, including means, medians, standard deviations, and ranges. Comparisons between the experimental and control group will be evaluated with univariate and multivariate logistic regression as appropriate. A conservative power analysis was performed and determined that a total of 118 (59 in each arm) would be required to achieve a power of 80% with an alpha error of 0.05 in order to detect a decrease in the rate of failed void trial from 30% to 10%. To account for a 15% dropout rate we will recruit 136 participants.

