## **Procedures**

- Once patients are enrolled and consents are obtained, they will be randomized into either tamsulosin or placebo group
- Investigational drug services will provide medication to the study investigators who will provide patients with their medication at the preoperative visit, which is typically 1-2 weeks prior to surgery.
- Patients will be instructed to take one pill by mouth daily for three days prior to surgery.
- While hospitalized after surgery, patients will continue to take their study medication. They will take one extra pill the morning after surgery, 3-4 hours prior to their voiding trial. Other than this one extra dose, they will continue taking one pill every evening after dinner until their medication has run out. This will total 3 days prior, and 6 days after surgery.
- The voiding trial, which is standard practice after urogynecologic surgery, will be performed the morning after surgery. This will include filling the bladder with 300cc of normal saline or sterile water retrograde through the foley catheter, then removing the catheter. The patient will have 15 minutes to void. The volume of their void will be measured. If they void 200ml or greater, they have passed the voiding trial. If they void less than 200ml or cannot void at all, they have failed the voiding trial and the catheter is reinserted with plans to remove it in the office in 4-6 days. If the void is not measured or cannot be measured for any reason, an ultrasound of the bladder will be performed to determine the post-void residual volume in the bladder with a threshold of must void 2/3 of instilled volume.
- The patient will complete the Voiding Symptom Survey at time of enrollment and again on postoperative day 4. They will be provided with a copy of this form prior to their discharge from the hospital. They will be contacted via telephone to report their results.

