- Data collected will include: Study number, MRN, age, race, BMI, current tobacco use, parity, ASA class, preoperative history of urinary retention, preoperative prescription for medication for overactive bladder or urge incontinence, urodynamic testing results (presence of stress urinary incontinence and detrusor activity, increased EMG recruitment, post-void residual, peak flow rate, detrusor pressure at peak flow rate), preoperative diagnosis particularly of stress urinary incontinence or pelvic organ prolapse, surgery performed, surgical complications, estimated blood loss, voiding trial results, presence of POUR, time until resolution of POUR, presence of postoperative urinary tract infection, results of postoperative Voiding Symptom Survey.

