## **OUTCOMES:**

**PRIMARY OUTCOME:** pass/fail of voiding trial on the morning after surgery

**SECONDARY OUTCOMES:** development of POUR at any time after surgery, diagnosis of urinary tract infection after surgery, Voiding Symptom Survey score

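### No suitable model is stated for the Voiding Symptom Survey score, and the enrolment score has no role; the uncut day-4 score should be analysed with the enrolment score as covariate

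*Combined protocol and SAP*

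**What the plan says.** The Outcomes section lists among the secondary outcomes "diagnosis of urinary tract infection after surgery, Voiding Symptom Survey score". It gives no cut-off, time point or change definition for the score.

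On timing, Procedures says: "The patient will complete the Voiding Symptom Survey at time of enrollment and again on postoperative day 4". The list of data to be collected, also under Procedures, names only "results of postoperative Voiding Symptom Survey"; the enrolment score does not appear there.

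On analysis, Statistical considerations says: "Comparisons between the experimental and control group will be evaluated with univariate and multivariate logistic regression as appropriate". It names no covariates. The same section also says: "Data will be evaluated with descriptive statistics, including means, medians, standard deviations, and ranges". Those are summaries, not a comparison of arms.

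Two other statements bear on the day-4 score. After an unsuccessful voiding trial, Procedures says of patients: "they have failed the voiding trial and the catheter is reinserted with plans to remove it in the office in 4-6 days". On missing data, Data security says: "If no data is obtainable, said data point will not be placed in statistical analysis and reported as such".

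**The concern.** Logistic regression in its usual form needs a binary response. It suits voiding-trial failure, later retention and urinary tract infection. For a score, the plan leaves open whether to keep it uncut, treat it as ordinal or cut it, and if cut, where. It also leaves open whether the enrolment value enters as a covariate, is subtracted, or is ignored. These choices change the power of the comparison, and with nothing written down they could be made after the data are seen.

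The enrolment survey is a measurement the patients are already asked to make. If it predicts the day-4 score, leaving it out of the model gives away precision. If it does not, including it costs almost nothing. At stake is the precision and credibility of one secondary comparison.

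**Working it through.** **Inputs from the documents.** 59 per arm, alpha 0.05, 80% power, and failed-trial rates of 30% and 10% (Statistical considerations); survey at enrolment and day 4, and catheter removal planned 4 to 6 days after reinsertion (Procedures).

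**Assumptions not in the documents.** Two-sided testing; a normally distributed score; a true difference of 0.5 SD; baseline to day-4 correlation r from 0.1 to 0.6.

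**The plan's own figure.** Unpooled two-proportion formula: (1.960 + 0.842)² × (0.3×0.7 + 0.1×0.9) / 0.2² = 58.87, so 59 per arm. The stated size reproduces with a two-sided 5% test. It rests on the binary primary outcome; nothing below changes it.

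**Power for the uncut score, 59 per arm (noncentral t).**
- Unadjusted: noncentrality 0.5 / √(2/59) = 2.716 on 116 df, power 76.8%.
- ANCOVA: residual variance multiplied by 1 − r², one df fewer. At r = 0.5 the noncentrality is 2.716 / √0.75 = 3.136, power 87.5%.
- Change score: variance multiplied by 2(1 − r). At r = 0.5 this factor is 1, so nothing is gained.

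| r | ANCOVA power | Change-score power | Difference detectable at 80% power, ANCOVA |
|---|---|---|---|
| 0.1 | 77.2% | 51.9% | 0.52 SD |
| 0.2 | 78.5% | 56.7% | 0.51 SD |
| 0.3 | 80.6% | 62.4% | 0.50 SD |
| 0.5 | 87.5% | 76.8% | 0.45 SD |
| 0.6 | 92.0% | 85.3% | 0.42 SD |

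Unadjusted, the detectable difference is 0.52 SD. ANCOVA beats the change score at every r shown, and below r = 0.5 the change score does worse than ignoring baseline.

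**If the score were cut at the median.** With the cut at the control median, the proportions above it are 50.0% and Φ(−0.5) = 30.9%, giving 56% power at 59 per arm. With the cut midway between the arm means they are 59.9% and 40.1%, giving 57% by normal approximation and 58–59% by simulated logistic regression (8,000 runs). Allowing for a further check near 60%, the range is 56–60%, about 17 to 20 points below the uncut comparison.

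**If the score is ordinal.** Simulated proportional-odds regression (4,000 runs; the skewed 7-level score is an assumption) had about 70% power unadjusted. Adding the enrolment score gained 0.2, 1.2, 4.5, 9.4 and 13.4 points at latent r = 0.1, 0.2, 0.3, 0.5 and 0.6. The loss from cutting given above is for a normal score and does not carry over to this case.

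**Catheter on day 4.** Expected failures: 59 × 0.30 = 17.7 control and 59 × 0.10 = 5.9 tamsulosin, about 18 + 6 = 24 of 118. This is an upper bound, since removal could come on day 4 itself and a catheter need not prevent a score.
- Precision: if all 24 gave no usable score (41 and 53 left), unadjusted power would be 66.2%, and ANCOVA 66.7%, 70.3%, 78.4% and 84.5% at r = 0.1, 0.3, 0.5 and 0.6.
- Bias, as an illustration: suppose tamsulosin has no effect on the score, failures are the top 30% or 10% of a latent standard normal cause, and the enrolment score is unrelated to that cause. The mean of the latent cause among those retained is −0.3477/0.70 = −0.497 in control and −0.1755/0.90 = −0.195 in tamsulosin, a gap of 0.302. If the score correlates 0.3 or 0.5 with the cause, the spurious difference against tamsulosin is 0.302 × 0.3 = 0.09 SD or 0.302 × 0.5 = 0.15 SD. Simulation gives the same values with ANCOVA.

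**The case against.** A reader might infer that the named method forces the score to be cut, and that the plan therefore loses nearly 20 points of power. The documents do not support that. They never say the score will be cut. The wording also admits an ordinal logistic model, or logistic regression of arm on the uncut score. In simulation the latter had about 78–80% power unadjusted, level with the uncut comparison; its odds ratio is awkward to interpret and I do not recommend it, but it shows that no cut is implied. The qualifier that ends the sentence, and the means and standard deviations listed beside it, also fit an uncut score. What remains is that no model is specified.

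The gain from baseline adjustment may also be close to nil. Surgery falls between the two measurements, the documents give no correlation, and at r = 0.1 the gain is 0.4 points. That is right, and it limits the claim.

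A reader might further infer that 24 women will have no score. Nothing says a woman with a catheter cannot answer, and results are reported by telephone. Only the possibility of unequal loss stands, and it is a separate matter that baseline adjustment does not solve.

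Finally, this is one secondary outcome with no power claim attached. That is a reason for low priority, not for leaving the model unstated.

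**Conclusion.** The point holds as a gap in specification with an inexpensive improvement. The plan states no model suited to the survey score and gives the enrolment score no role, and Procedures has the survey completed at enrolment while its data list names only the postoperative result. Under the stated assumptions, adjustment adds between 0.4 points of power (r = 0.1) and about 15 points (r = 0.6). The effect size, correlation and score distribution are all assumed, so these figures show a range and are not an estimate for this trial. The loss from a median cut is conditional on a choice the documents do not make. Any bias from unequal loss of day-4 scores would remain after the change. The primary outcome and the 118 stand. Priority: lower, a secondary-analysis clarification.

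**What to change.** Before the data are analysed:

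1. In Statistical considerations, state that the uncut day-4 survey score will be compared between arms by ANCOVA with the enrolment score as covariate, or by proportional-odds regression with the same covariate if the score is ordinal or strongly skewed. Say in advance which applies. Report the adjusted difference or odds ratio with its 95% CI. Use neither a cut score nor a plain change score. Keep logistic regression for the binary outcomes.
2. Add the enrolment score to the data list in Procedures, so that the two parts of that section agree.
3. State a simple rule for a missing enrolment score, such as filling in the overall baseline mean, so that no patient with a day-4 score is dropped.
4. Report the number of usable day-4 scores per arm and, for women without one, their voiding-trial result. This makes any unequal loss visible; it does not correct it.

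The cost is a few sentences, one data field and one degree of freedom. No extra patients or visits are needed.

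### Recruiting 136 covers about 13% dropout, not the stated 15%: at 15% about 115–116 participants remain, against the 118 the plan requires

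*Combined protocol and SAP*

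**What the plan says.** The Statistical considerations section of the combined protocol and SAP gives the required number as "a total of 118 (59 in each arm) would be required to achieve a power of 80% with an alpha error of 0.05". The target difference is to "detect a decrease in the rate of failed void trial from 30% to 10" percent. The next sentence sets the recruitment target: "To account for a 15% dropout rate we will recruit 136 participants". No inflation formula is shown, and the plan does not say what the 15% is a percentage of.

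The primary outcome, under Outcomes, is "pass/fail of voiding trial on the morning after surgery". On missing data, the Data security section first commits staff to searching other electronic medical record sources and then says: "If no data is obtainable, said data point will not be placed in statistical analysis and reported as such". No imputation is described anywhere in the document.

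**The concern.** A dropout rate is ordinarily the fraction of enrolled participants who are lost. To end with a required number after losing a fraction d, the required number is divided by (1 − d). Multiplying it by (1 + d) always gives too few, because the losses come out of the larger, recruited number. The target of 136 looks like the product of the second method.

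If so, the plan's own dropout assumption takes it below the number it calls required. Missing outcomes are not imputed, so the analysis would not make up the difference. The stakes are modest: the shortfall is a few participants. But the sentence claims an allowance that the design does not deliver, any reader can check it by hand, and a trial report could carry it forward.

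**Working it through.** **Inputs, all from Statistical considerations:** 118 required in total, 59 per arm; power 80%; alpha 0.05; failure rates 30% and 10%; dropout 15%; 136 recruited. Sidedness and the formula are not stated. I assume a two-sided test.

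**Step 1. Reproduce the required number.** Two proportions, normal approximation, unpooled variance:

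n per arm = (z₀.₉₇₅ + z₀.₈₀)² × (0.3 × 0.7 + 0.1 × 0.9) / (0.3 − 0.1)² = 58.87, rounded up to 59, so 118 in total.

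This matches the plan. The arcsine formula gives nearly the same value (59.01), while the pooled two-sided formula gives 62 per arm. The plan's figure is therefore consistent with a two-sided unpooled calculation.

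**Step 2. Reproduce the recruitment target.**

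- Multiplying: 118 × 1.15 = 135.7, rounded up to 136. This matches the plan.
- Dividing: 118 / 0.85 = 138.8, rounded up to 139. For equal arms, 59 / 0.85 = 69.4, so 70 per arm and 140 in total.

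**Step 3. What 136 delivers at 15% dropout.**

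- Lost: 136 × 0.15 = 20.4.
- Remaining: 136 × 0.85 = 115.6, so 115–116.
- Shortfall against 118: 2–3 participants.

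**Step 4. The largest dropout that 136 covers.** Spare recruits: 136 − 118 = 18. As a share of those recruited, 18/136 = 13.2%. As a share of the 118 required, 18/118 = 15.3%.

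**Step 5. Effect on power.** Using the formula of Step 1, power = Φ(0.2 / √(0.21/n₁ + 0.09/n₂) − 1.96), where n₁ is the control arm and n₂ the tamsulosin arm:

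| Evaluable | Per arm | Power |
|---|---|---|
| 118 | 59 / 59 | 80.1% |
| 116 | 58 / 58 | 79.4% |
| 115.6 | 57.8 / 57.8 | 79.3% |
| 115 | 57 and 58 | 78.9–79.2%, depending on which arm has 57 |

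The loss at 57.8 per arm is 80.1 − 79.3 = 0.8 percentage points. The pooled formula gives 78.2% at 59 per arm and 77.4% at 57.8, a loss of the same size. The level of power depends on the formula; the loss hardly does.

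**The case against.** Nobody need dispute the arithmetic. The case on the other side concerns its reading and its weight.

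- **The denominator is undefined.** If the 15% is taken of the 118 required, the allowance is 0.15 × 118 = 17.7, or 18 extra, and 136 is exactly right. That reading is possible, but the plan does not state it and it is not the usual meaning. A reader would still take 136 to be enough if 15% of enrolled participants were lost.
- **Dropout need not mean a missing primary outcome.** The voiding trial takes place in hospital the morning after surgery and is standard practice. Someone who stops the study medication or misses the later survey could still have a result, and record searches may recover others. This stands as a caution, because the plan does not define dropout. But an allowance added to an evaluable number only makes sense as an allowance for participants without the outcome. Study drug is handed out typically 1–2 weeks before surgery, so a participant who leaves before the operation would have no voiding trial to retrieve.
- **The effect is very small.** The gap is 2–3 participants and under one point of power, around a 15% figure for which the plan cites no source. This is correct, and it is why the point is minor.
- **The 79% depends on an inferred formula.** It does: the pooled formula gives 77.4%. The unpooled formula is the natural basis here because it reproduces the plan's own 59 per arm at 80%, but the formula should be named wherever the figure is used.

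**Conclusion.** The concern holds, at minor severity. On the ordinary meaning of a dropout rate, 118 required, 15% dropout and 136 recruited cannot all be true together, and nothing elsewhere in the document reconciles them. At 15% dropout the trial would have 115–116 evaluable participants and lose about 0.8 points of power.

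This rests on two readings: that the 15% is a share of those recruited, and that a dropout is someone without a primary outcome. The power figures also assume a two-sided test and the unpooled formula. The discrepancy does not threaten the trial's conclusions; it is a stated allowance that needs correcting.

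**What to change.** Keep 136 and replace the sentence with, for example: *We will recruit 136 participants, which allows for about 13% dropout; at 15% dropout, 115–116 would be evaluable and power would be about 79% (two-sided, unpooled normal approximation).*

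This changes one sentence. It needs no extra recruits and alters no procedure; the only cost is a slightly less favourable stated allowance. If the sponsor did mean 15% of the 118 required, saying so in that sentence would also remove the conflict. Holding to both 118 evaluable and 15% of recruits lost would mean recruiting 139, or 140 for equal arms, but a loss of under one point of power does not call for that.

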## **OUTCOMES:**

**PRIMARY OUTCOME:** pass/fail of voiding trial on the morning after surgery

**SECONDARY OUTCOMES:** development of POUR at any time after surgery, diagnosis of urinary tract infection after surgery, Voiding Symptom Survey score

